| | 
 • Patients who do not use Catalan, Spanish, English, Portuguese, Italian, Dutch, German, Swedish, Hungarian, Romanian, or French. • Patients without a mobile phone • Patients without internet connection • Patients with moderate or severe cognitive impairment without a competent caregiver. • Patients with severe psychiatric illness. • Patients with planned cardiac surgery. • Patients with planned heart transplant or LVAD implant. |
| Recruitment strategy: | When a patient is eligible according to the criteria, he/she must complete the informed consent provided on day 0. Each hospital will decide when to include their patients according to their particular clinical practice (either in the process of discharge planning or during the first follow-up visit, i.e.. 1 or 2 weeks after discharge). Patients will be monitored for 6 months, with a recruiting period of 6 months. The last subject included will then finish the study after one year from the first day of the study. |
| Data Analysis: | There is no power calculation associated with the study since it is an observational study. Once the algorithms are developed, model performance in terms of accuracy will be evaluated by means of C statistic, area under the receiver operating characteristic curve, and creation of a calibration plot. Furthermore, the models will be evaluated in terms of fairness and potential bias using metrics including statistical parity, group fairness, equalized odds, and predictive equality. |
| Study Schedule: | February - March 2023: CEIm approval April 2023: study kick-off October 2023: recruitment period completed. April 2024: last patient, last visit May 2024: results analysis and final report draft |

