5.2 Primary and secondary endpoints

Primary endpoints

- Creation of a labeled and diverse dataset from a multicenter perspective. The dataset will contain the following data:
 - Physiological parameters: heart rate, calories consumed, steps count, physical activity, oxygen saturation, heart rate variability measurements, stress levels, sleep tracking data, systolic and diastolic blood pressure, weight, BMI
 - Socio-demographic data: sex, age, ethnic group, employment, level of education, number of people living with the patient, caretaker.
 - Risk factors: comorbidities, diabetes, hypertension, smoking, alcohol consumption, heart disease history
 - Medication tracking: lipid-lowering medication, PCSK9 inhibitors, beta-blockers, anticoagulation agents, ACE inhibitors, anti-arrhythmic drugs, anti-inflammatory drugs, aldosterone antagonists, angiotensin receptor/neprilysin inhibitor, other diuretics
 - Symptomatology questionnaire for patients
 - NYHA-class
 - Left Ventricular Ejection Fraction (LVEF)
 - Clinical interventions: hospital readmission, mortality, UCI visits
 - Health questionnaire answers: self-care, quality of life
 - Classified alarms with their respective timestamp and annotation by the medical professionals
 - Measurement ranges for each personalized alarm and their changes

- Implementation of ML models to improve the current alarm-based system using the dataset created. The models should:
 - Provide a relevance level for each new alarm by reducing the number of irrelevant alarms and thus fostering personalized follow-up.
 - Be robust across different new hospitals and reliable and fair across different target populations, considering the diverse sociodemographic data that will be available in the dataset.

Secondary endpoints

- Development and implementation of ML event prediction algorithms that will add new self-generated alarms to the system. These alarms should forecast:
 - Untracked hospital interventions, such as UCI visits or hospital readmissions.
 - Changes of medication with their particular estimated dose.
 - Clinical events, such as mortality.
- Assessment of patient and medical professional's satisfaction with and usability of the digital platform at the end of the study by means of the "System Usability Scale" (SUS) (Brooke, 1986) and the "Post-Study Usability Questionnaire" (PSSUQ).

6 Subjects/population(s)

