6.3 Criteria for withdrawal/discontinuation of participants

There are several situations in which the participant may be withdrawn from the study, including the development of an exclusion criterion during the execution of the study, withdrawal of informed consent, and when the participant is unwilling to continue the study.

The withdrawn participants do not have to be replaced.

If the participant withdrawals from the study, his/her data must be anonymized at the end of the study. This anonymization is not performed if the participant gives explicit consent. For the protection of the withdrawn participant, he/she must be provided with the standard follow-up care designated by his/her respective medical professional.

7 Statistical analysis plan and power calculation

Machine learning models are data-hungry models. This means that the performance of the model will potentially increase with the increase of the dataset and classified events in each classification class. We could simplify the classification task by categorizing alarms as relevant or irrelevant, thus reducing it to a binary classification problem. We will probably have to deal with an unbalanced problem as we might receive a lot of irrelevant classified alarms and few relevant ones. In an unbalanced classification problem as in our case, the best measurements to assess model performance are precision and sensitivity. Precision is defined as the fraction of well-classified instances from class A among all instances that were classified as class A. Sensitivity instead is defined as the fraction of instances from class A that were classified as pertaining to class A. A recent study by Juba and Le (Juba and Le, 2019) proved that even using data augmentation techniques to deal with an unbalanced dataset, adding more training data is the best solution for measuring precision and recall.

Furthermore, we pretend to train the algorithm not just to solve the binary classification problem but also to be able to give specific recommendations in terms of changes in medication, hospital readmissions, and others. Thus, the sample size might have to be big enough to cover a huge range of possible outcomes.

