For instance, a similar study (Koulaouzidis et al., 2016) with 308 HF patients telemonitored for around 9 months predicted whether patients would undergo hospital readmission during the following day based on the day-to-day physiological measurements of each patient. Performance accuracy was high. However, more specific measures such as the sensitivity were very low, putting patients at a high risk of misclassification.

During model development and training, k-fold cross-validation will be implemented to fine-tune the model parameters and ensure robustness. Additionally, part of the data won't be used during training and validation in order to test model performance on new data never seen by the algorithm. After the implementation of the AI system into the platform, a randomized controlled trial will be carried out in hospitals that didn't participate in the present observational study to externally validate the ML models. In this future study, a quantitative sample size evaluation will be possible by comparing clinical outcomes between the control and study group.

Therefore, the sample size for the present study has been determined qualitatively taking into consideration the reasons mentioned above, that during the 3 first months after HF decompensation is when patients present more harmful events, and the budget available for the project. The plan is to include the maximum number of participants while accomplishing a relevant socio-demographic diversity in the final cohort. We consider that a total of 500 patients will give sufficient data diversity and classified events (alarms + unexpected interventions) to ensure a robust model performance.

Once the algorithms are developed, model performance in terms of accuracy will be evaluated by means of C statistic, the area under the receiver operating characteristic curve, and by creating a calibration plot. Furthermore, we will evaluate the models in terms of fairness and potential bias using metrics such as statistical parity, group fairness, equalized odds, and predictive equality.

8 Conduct

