8.2 Study management, study monitoring, data and sample management

8.2.1 Study management and clinical procedures.

- Recruitment phase: once the CEIm protocol has been approved for each hospital, the assigned medical professionals responsible for the study will be in charge of including patients in the study, following the inclusion criteria. They will explain the study characteristics to the patient and ask if they are willing to be included in the study. The patient will sign the informed consent that includes the acceptance to use active and passive data. Once accepted, the medical professionals will register the user into the platform, fill in all the data required about their socio-demographics and risk factors, and will train the patient on the proper use of the app and devices. The specific calendar for each hospital will depend on its particular involvement and protocol approval date.
- Execution of the study: during the study, patients and medical professionals will evolve as mentioned below.

- **Day 0:** First visit and study enrollment either before or after HF hospital discharge or HF decompensation. This first visit will include,
 - Explanation of the study to the patient and doubt clarification
 - Explanation of the terms and conditions, and signature of the informed consent
 - Medical professionals will register the patient to the HumanITcare platform together with their personal credentials. They will train patients on the proper use of the app and medical devices.
 - Patients will be given a blood pressure monitor, a smartwatch and, a pulse oximeter. Devices will be synchronized with the app (or with the provider's app in some cases). The patient should wear the smartwatch during the entire study period, charging its battery whenever it is about to run out and putting it back on just after it is fully charged.
 - Registration of the following patient variables into the platform by the medical professional:
 - Socio-demographic data: Age, sex, ethnic group, employment, education level, caretaker, number of people living with the patient
 - Risk factors: Comorbidities, diabetes, hypertension, smoking, alcohol consumption, heart disease history
 - Height
 - New York Heart Association (NYHA) Functional Classification
 - Left Ventricular Ejection Fraction (LVEF)
 - Medication use and doses

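### Section 7 does not say at what level the C statistic is computed or how data are split, and plans no within-patient measure, so a lack of alarm-level discrimination could go unseen

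*Combined protocol and SAP*

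**What the plan says.** The first task of the primary models in section 5.2 is to "Provide a relevance level for each new alarm by reducing the number of irrelevant alarms and thus fostering personalized follow-up". Alarms are nested in patients: monitoring lasts 6 months with daily or continuous measurements (section 8.2.3, Table 1), and the dataset holds "Measurement ranges for each personalized alarm and their changes". Many predictors are fixed or nearly fixed for a patient, for example "Socio-demographic data: Age, sex, ethnic group, employment, education level, caretaker, number of people living with the patient", together with risk factors, NYHA class and LVEF at day 0 (section 8.2.1).

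On evaluation, section 7 states that "model performance in terms of accuracy will be evaluated by means of C statistic, the area under the receiver operating characteristic curve", adds a calibration plot, and lists four kinds of group fairness metric. The synopsis (Data Analysis) repeats this: "area under the receiver operating characteristic curve, and creation of a calibration plot". Earlier in section 7, precision and sensitivity are called the best measures for the unbalanced alarm task, because "we might receive a lot of irrelevant classified alarms and few relevant ones", but the closing evaluation sentence does not take them up.

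On development, "k-fold cross-validation will be implemented to fine-tune the model parameters and ensure robustness", and a part of the data is kept back for testing. Neither document section gives the unit of the folds or of the hold-out (alarm, patient or hospital), the level of the C statistic, a reference model, or any treatment of repeated alarms within a patient.

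**The concern.** A C statistic is the probability that a randomly chosen relevant alarm scores higher than a randomly chosen irrelevant one. Taken over all alarms of 500 patients, nearly every such pair comes from two different patients. Knowing which patients tend to have relevant alarms is then enough for a respectable value, even if the model cannot say which of one patient's alarms matters. Section 5.2 asks for that second ability when it speaks of each new alarm and of personalised follow-up.

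The undefined split raises a related problem. If a patient's alarms fall on both sides of the hold-out, a model can learn the patient's relevance rate in training and be rewarded for it in testing. Section 5.2 requires robustness in new hospitals, where no patient has been seen before.

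At stake is what the study can conclude about a primary endpoint, and about models that are to be built into the platform and then taken into a randomised trial.

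**Working it through.** The plan gives no target AUROC, prevalence, alarm count or variance, so there is no figure to reproduce. Only the 500 patients come from the documents; every other input below is an assumption.

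**1. Exact case.** Let half the patients have a relevant fraction p1 and half p2, with equal alarm counts, and give every alarm its patient group's score. Counting ties as one half:

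AUROC = [p1(1−p2) + ½{p1(1−p1) + p2(1−p2)}] / [(p1+p2)(2−p1−p2)]

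- p1 = 0.20, p2 = 0.02: [0.196 + ½(0.160 + 0.0196)] / (0.22 × 1.78) = 0.2858/0.3916 = 0.73.
- p1 = 0.15, p2 = 0.05: [0.1425 + ½(0.1275 + 0.0475)] / (0.20 × 1.80) = 0.23/0.36 = 0.64.

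Within any one patient all scores are tied, so the within-patient AUROC is exactly 0.50.

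**2. Weight of same-patient pairs.** In the 0.20/0.02 case with m alarms each, same-patient pairs number 250 m²(0.160 + 0.0196) = 44.9 m². All pairs number (250 × 0.22 m)(250 × 1.78 m) = 24,475 m². The share is 0.18%. The simulations below give 0.2% to 0.3%.

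**3. Simulation.** 500 patients; mean 30 alarms each (negative binomial); 10% relevant; logit P(relevant) = a + u (patient) + w (alarm), with SD(w) = 1.0; 12 repetitions.

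| SD(u) | Patient-only, pooled | Patient-only, 30% of patient variance explained, pooled | Alarm-only, pooled | Both, pooled | Patient-only, within | Alarm-only, within |
|---|---|---|---|---|---|---|
| 0.5 | 0.62 | 0.57 | 0.75 | 0.77 | 0.50 | 0.75 |
| 1.0 | 0.72 | 0.62 | 0.73 | 0.82 | 0.50 | 0.75 |
| 1.5 | 0.81 | 0.68 | 0.71 | 0.87 | 0.50 | 0.75 |

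A second setting (mean 60 alarms, 15% relevant, SD(w) = 0.8) gives 0.62/0.73/0.81 for the patient-only score, again with 0.50 within patient.

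**4. Would another planned metric show it?**
- *Calibration plot:* no. A correct patient-level risk is calibrated when pooled: among alarms given risk p, a fraction p is relevant.
- *Fairness metrics:* no. They compare groups of patients, not alarms of one patient.
- *Pooled precision and sensitivity:* no. In the 0.20/0.02 case, flagging every alarm of the first group gives sensitivity 0.20/0.22 = 91% and precision 20%, against a base rate of 11%, with no ranking inside any patient.

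**5. Split by alarm.** With no alarm-level signal at all and an 80/20 split by alarm, shrunken patient means from the training part score about 0.60/0.72/0.81 on the held-out alarms (SD(u) 0.5/1.0/1.5). For new patients the value is 0.50.

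**The case against.** A reader might infer that the plan judges its models by a single pooled AUROC, chooses among them on it, and will therefore pick a useless model. The documents do not support this. They leave the level of the C statistic open, name no score for model selection, set no AUROC threshold for success, and also mention precision, sensitivity, calibration and fairness.

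Nor is the wrong pick a general result. A patient-only score outranks an alarm-only score on pooled AUROC only when between-patient variation is large relative to the alarm signal and well enough predicted. With SD(w) = 0.8 and 15% relevant:

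- Patient SD 0.5, fully predicted: 0.628 against 0.702, no reversal.
- Patient SD 1.0, half the variance explained: 0.663 against 0.685, no reversal.
- Patient SD 1.5, 30% explained: 0.667 against 0.665, a tie.

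The dataset holds both static and daily data, so the natural candidate uses both. Such a model had the highest pooled AUROC in every setting examined.

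Ranking between patients is also part of the task. In the exact case, silencing the low-rate group removes 0.98/1.78 = 55% of irrelevant alarms, which is of some use. For mortality forecasts, a same-patient comparison would drop every survivor and so could not serve as the main measure.

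Finally, the documents do not say that the split is by alarm, and a later trial in other hospitals offers a further check. That trial comes after the models have been built, however, and its stated comparison is of clinical outcomes between arms.

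All of this stands, and it limits the point to what the planned evaluation can reveal. It does not remove the gap: no planned figure would separate a model that ranks a patient's alarms from one that does not.

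**Conclusion.** The point holds in this form: the level of the C statistic and the splitting unit are undefined, and neither a within-patient measure nor a static reference model is planned for an endpoint defined per alarm. On the conventional reading, a score with no within-patient ability can show an AUROC of about 0.62 to 0.81, or 0.57 to 0.68 if static data explain 30% of the patient variance (SD(w) = 1.0, 10% relevant). If the hold-out is drawn by alarm, memorising patients alone can show about 0.60 to 0.81. These sizes rest on assumed patient SDs of 0.5 to 1.5 and assumed alarm counts and prevalences. The 0.50 within patient does not depend on them. The evaluation can mislead; the documents do not establish that it will. This is a cheap improvement that goes beyond wording, because it changes what can be concluded about the primary machine-learning endpoint.

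**What to change.** In section 7, before any results are seen:

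1. State the level of the C statistic. For alarm relevance, report a within-patient C statistic (relevant/irrelevant pairs from the same patient) beside the pooled one, not in its place. Keep the pooled measure as the main one for mortality and other rare-event forecasts.
2. On the hold-out, report each model's gain over a benchmark that uses only day-0 data and hospital.
3. Keep all of a patient's alarms in one fold and on one side of the hold-out, and bootstrap confidence intervals by patient.

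The cost is plan wording and a few lines of code, with no new data. The reported figures will look less favourable. Patients whose alarms are all of one class do not contribute to the within-patient measure, so their number should be reported with it.

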8.1 Summary of the study schedule

| | |
|---------------------------|--|
| September 2022 | Kick-off. First meeting with Hospital de Torrevieja, the study leaders. |
| September - December 2022 | Partners selection and coordination. Discussion of protocol design and alarm system configuration. |
| January - March 2023 | CEIms approvals |
| April 2023 | Study kick-off. Register investigators on the platform. Initiate patient recruitment. |
| April 2023 | First patient - first visit |
| October 2023 | First patient - last visit |
| October 2023 | Last patient - first visit |
| April 2024 | Last patient - last visit |
| May 2024 | Results analysis and final report draft |
| June 2024 | Improvement of the ML models |

Please note that these are preliminary dates that may be subject to change during the execution of the clinical study.

8.2 Study management, study monitoring, data and sample management

8.2.1 Study management and clinical procedures.

- Recruitment phase: once the CEIm protocol has been approved for each hospital, the assigned medical professionals responsible for the study will be in charge of including patients in the study, following the inclusion criteria. They will explain the study characteristics to the patient and ask if they are willing to be included in the study. The patient will sign the informed consent that includes the acceptance to use active and passive data. Once accepted, the medical professionals will register the user into the platform, fill in all the data required about their socio-demographics and risk factors, and will train the patient on the proper use of the app and devices. The specific calendar for each hospital will depend on its particular involvement and protocol approval date.
- Execution of the study: during the study, patients and medical professionals will evolve as mentioned below.

- **Day 0:** First visit and study enrollment either before or after HF hospital discharge or HF decompensation. This first visit will include,
 - Explanation of the study to the patient and doubt clarification
 - Explanation of the terms and conditions, and signature of the informed consent
 - Medical professionals will register the patient to the HumanITcare platform together with their personal credentials. They will train patients on the proper use of the app and medical devices.
 - Patients will be given a blood pressure monitor, a smartwatch and, a pulse oximeter. Devices will be synchronized with the app (or with the provider's app in some cases). The patient should wear the smartwatch during the entire study period, charging its battery whenever it is about to run out and putting it back on just after it is fully charged.
 - Registration of the following patient variables into the platform by the medical professional:
 - Socio-demographic data: Age, sex, ethnic group, employment, education level, caretaker, number of people living with the patient
 - Risk factors: Comorbidities, diabetes, hypertension, smoking, alcohol consumption, heart disease history
 - Height
 - New York Heart Association (NYHA) Functional Classification
 - Left Ventricular Ejection Fraction (LVEF)
 - Medication use and doses
 - Patients will answer first the European Heart Failure Self-Care Behaviour Scale (EHFScB scale), the Quality-of-life SF-12 and the Mobile Device Proficiency questionnaires through the app.
- **Day 0 until the end of the study:** Registration of measurements and questionnaires: Patients will be notified through the app whenever they need to register a measurement or answer a health questionnaire. Weight, blood pressure (systolic and diastolic) and oxygen saturation (through the pulse oximeter) will be registered daily. Times for each registration are specified below. Smartwatch device measurements are automatically registered once synchronized with the app. Health questionnaires will be delivered periodically through the app to the patient. Specifically, the symptomatology questionnaire will be delivered twice a week (on Mondays and Thursdays) and the self-care and quality-of-life questionnaires will be answered periodically (specified below).
- **Day 0 until the end of the study:** Medical professionals will follow up on patient's adherence to the study by checking their measurements and health questionnaire answers through the platform. Clinicians will make a control call in case of missing data.
- **Day 0 until the end of the study:** Medical professionals are required to annotate each alarm whenever they receive it and check its relevance. If they are unable to evaluate it at the time of appearance, they are allowed to do it later. However, we strongly recommend annotating the alarms, if there are

any, on a daily basis. Annotations will include adding information about the relevance of an alarm by assessing the health status of the patient.

- **Day 0 until the end of the study:** Medical professionals must report every hospital readmission, mortality, emergency department visit or non-fatal HF decompensation of each patient whenever it happens through the platform. If they are unable to register the event at the moment, events can be registered later on through the platform with their corresponding date/s and duration.
- **Day 0 until the end of the study:** Medical professionals are required to report every medication change through the platform, both due to an alarm-derived decision or derived from a clinical evaluation.
- **Day 7 to 10:** First follow-up visit: Medical professionals will cite the patients for in-person follow-up visits.
- **Day 90 (3 months):** Second follow-up visit: Medical professionals will cite the patients for in-person follow-up visits.
- **Day 180 (6 months):** Last follow-up visit and end of the study: The patient monitoring will finish after 6 months from inclusion to the study (first hospital discharge). Patients should answer the European Heart Failure Self-Care Behaviour Scale (EHFScB scale), the Minnesota Living with Heart Failure questionnaire, the Mobile Device Proficiency Questionnaire, the “System Usability Scale” (SUS) and the “Post-Study Usability Questionnaire” (PSSUQ). Then, they will be required to return the medical devices and medical professionals will change the status of the patient to “finished” on the platform.
Medical professionals will be asked to answer the SUS and PSSUQ questionnaires at the end of the whole study period.
- Medical professionals may cite patients for more in-person visits depending on the specific clinical practice of each center.

